#### 5.1.5 Part E

The combination of nivolumab 1 mg/kg and ipilimumab 3 mg/kg will be administered every 3 weeks X 4 followed by nivolumab 3 mg/kg administered every 2 weeks until off protocol criteria in Section 10.1 are met. Note that cycle length is 21 days for the first 4 cycles of Part E; in cycle 5 and for subsequent cycles, cycle length will be 28 days and nivolumab 3 mg/kg will be administered

on days 1 and 15 of each cycle.

Dose Level	Cycles 1-4 (21-day Cycles)	Cycles 5+ (28-day Cycles)
1	Nivolumab (IV over 30 min) 1 mg/kg on Day 1  Ipilimumab (IV over 90 min) 3 mg/kg on Day 1	Nivolumab (IV over 30 min) 3 mg/kg on Days 1 and 15

Infusion of ipilimumab (over 90 minutes) should be initiated no sooner than 30 minutes after completion of the nivolumab infusion. If nivolumab therapy is withheld, ipilimumab should also be withheld.

Vital signs (temperature, pulse, blood pressure and respirations) will be monitored closely baseline then every 15 minutes x 2, then every 30 minutes x 3 beginning at the initiation of administration of ipilimumab infusion. Patients who develop symptoms or signs of hypotension ( $\geq 25\%$  decrease in systolic or diastolic blood pressures from baseline) that are temporally related to ipilimumab infusion will receive additional IV fluids as appropriate until the signs and symptoms resolve. During cycle 1, patients must remain for observation for a total of 6 hours following completion of ipilimumab. The post administration observation period may be extended to 24 hours and the patient admitted if clinically indicated. If the patient tolerates the first infusion of ipilimumab without incident, the observation period may be reduced to 90 minutes following completion of the drug infusion with subsequent cycles. Any patient who develops Grade 3 or 4 anaphylaxis felt to be primarily related to administration of ipilimumab will be removed from protocol therapy.

5.2 **Protocol therapy will continue to be administered until patient meets one of the off protocol criteria in [Section 10.1](#). Criteria for Starting Subsequent Cycles**

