A cycle may be repeated every 28 days for Parts A and B (and either every 21 days or 28 days for Parts C, D, and E) if the patient has again met the parameters as defined in the eligibility section, [Section 4.0](#), has not met any of the criteria for removal from therapy per [Section 10.1](#), and has not experienced a dose-limiting toxicity. A delay of up to 7 days from the date of the next scheduled treatment dose may be allowed. Please note the following exceptions:

- Patients may continue on to the next cycle if Pancreatic Function is  $\leq$  Grade 1 (See [Section 6.5](#))
- Patients who experience pleural effusion may continue onto the next cycle upon resolution as per [Section 6.8](#).

5.3 **Grading of Adverse Events**

Adverse events (toxicities) will be graded according to the NCI Common Terminology Criteria for Adverse Events (CTCAE) version 5.0. All appropriate treatment areas should have access to a copy of the CTCAE version 5.0. A copy of the CTCAE version 5.0 can be downloaded from the CTEP web site [http://ctep.cancer.gov/protocolDevelopment/electronic\\_applications/ctc.htm](http://ctep.cancer.gov/protocolDevelopment/electronic_applications/ctc.htm). Any suspected or confirmed dose-limiting toxicity should be reported immediately (within 24 hours) to the Study Chair.

5.4 **Definition of Dose-Limiting Toxicity (DLT)**

DLT will be defined as any of the following events that are possibly, probably, or definitely attributable to protocol therapy. DLT definitions will be the same for all parts. The DLT

observation period for the purposes of dose-escalation in Part C or dose de-escalation in Part A will be the first cycle of therapy. Toxicities with subsequent cycles will be monitored carefully and if significant numbers of delayed toxicities are observed, consideration will be given to a protocol amendment to focus on delayed toxicities in assessing the MTD.

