*Patients with purpuric or bullous lesions must be evaluated for vasculitis, Steven-Johnson syndrome, TEN, and autoimmune bullous disease including oral lesions of bullous pemphigus/pemphagoid. Pruritus may occur with or without skin rash and should be treated symptomatically if there is no associated liver or GI toxicity. Note skin rash typically occurs early and may be followed by additional events particularly during steroids tapering.	
Recommended management: See Skin AE Management Algorithm	

6.4.1 **BMS Recommended Skin Adverse Management Algorithm**

These suggested management guidelines are taken from the BMS algorithms provided in the Investigator's Brochure.

Toxicity (CTCAE v.5)	Management	Follow-up
Grade 1/2 Rash	
 
• Symptomatic therapy (e.g. antihistamines, topical steroids)
 
• Continue protocol therapy
 
	
If persists > 1-2 weeks or recurs:
 
 
• Consider skin biopsy
 
• Hold protocol therapy
 
• Consider 0.5-1 mg/kg/day methylprednisolone IV or oral equivalent
 
• Once improving, taper steroids over at least 1 month
 
• Consider prophylactic antibiotics for opportunistic infections
 
 
If worsens: Treat as Grade 3/4

Grade 3/4 Rash	
 
• Hold infusion
 
• Consider skin biopsy
 
• Dermatology consult
 
• 0.5-1 mg/kg/day methylprednisolone IV or IV equivalent
 
	
If improves to Grade 1:
 
 
• Taper steroids over at least 1 month,
 
• Add prophylactic antibiotics for opportunistic infections
 

Patients on IV steroids may be switched to an equivalent dose of oral corticosteroids (e.g. prednisone) at start of tapering or earlier, once sustained clinical improvement is observed. Lower bioavailability of oral corticosteroids should be taken into account when switching to the equivalent dose of oral corticosteroids.

6.5 **Dose modifications for Hepatic/Pancreatic Adverse Events**

Liver Function Elevation	Management/Next Dose of Nivolumab ± Ipilimumab
≤ Grade 1	Continue protocol therapy
Grade 2	Hold until baseline. If resolves within 7 days, resume at same

Liver Function Elevation	Management/Next Dose of Nivolumab ± Ipilimumab
	dose level.

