Grade 3	Off protocol therapy unless DLT exception in Section 5.4.1 is met.
Grade 4	Off protocol therapy unless DLT exception in Section 5.4.1 is met.
See Appendix IX for values that represent thresholds between CTCAE grades. Continued treatment of active immune mediated hepatitis may exacerbate ongoing inflammation. Holding drug to evaluate LFT changes and early treatment are recommended.	
LFT changes may occur during steroid tapers from other events and may occur together with other GI events including cholecystitis/pancreatitis.	
Recommended management: see for Hepatic AE management algorithm	

Pancreatitis; Amylase/Lipase	Management/Next Dose of Nivolumab ± Ipilimumab
≤ Grade 1	Continue protocol therapy
Grade 2 Amylase	Continue protocol therapy
Grade 2 Pancreatitis/Lipase	Hold until resolution to ≤ Grade 1; Resume at same dose level if asymptomatic
Grade 3	Off protocol therapy unless DLT exception in Section 5.4.1 is met.
Grade 4	Off protocol therapy
Patients may develop symptomatic and radiologic evidence of pancreatitis as well as DM and DKA. Lipase elevation may occur during the period of steroid withdrawal and with other immune mediated events or associated with colitis, hepatitis, and patients who have asymptomatic lipase elevation typically have self-limited course and may be retreated. For treatment management of symptomatic pancreatitis please follow the Hepatic Adverse Event Management Algorithm below	

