6.5.1 BMS Recommended Hepatic Adverse Event Management Algorithm

These suggested management guidelines are taken from the BMS algorithms provided in the Investigator’s Brochure.

Consider imaging for obstruction.

Toxicity (CTCAE v.5)	Management	Follow-up
Grade 1* AST or ALT, and/or bilirubin increased	
 
Continue protocol therapy
 
	
 
Continue routine LFT monitoring per Table 8.1
 
 If worsens: 
 
Treat as Grade 2 or 3/4
 

Toxicity (CTCAE v.5)	Management	Follow-up
Grade 2* AST or ALT, and/or bilirubin increased	
 
• Hold infusion
 
• Increase LFT monitoring to every 3 days
 
	
If improves to baseline:
 
 
• Continue routine LFT monitoring per Table 8.1
 
• Resume protocol therapy
 
 
If elevations persist >5-7 days or worsen:
 
 
• 0.5-1 mg/kg/day methylprednisolone IV or oral equivalent
 
• When LFT returns to grade 1 or baseline, taper steroids over at least 1 month
 
• Consider prophylactic antibiotics for opportunistic infections
 

Grade 3 or 4* AST or ALT, and/or bilirubin increased	
 
• Discontinue protocol therapy
 
• Increase LFT monitoring to every 1-2 days
 
• 1-2 mg/kg/day methylprednisolone IV or oral equivalent**
 
• Add prophylactic antibiotics for opportunistic infections
 
• Consult gastroenterologist
 
	
If improves to Grade 2:
 
 
• Taper steroids over at least 1 month
 
 
If does not improve in > 3-5 days, worsens or rebounds:
 
 
• Add mycophenolate mofetil 600 mg/m^2/dose (max 1 g/dose) BID
 
• If no response within an additional 3-5 days, consider other immunosuppressants per local guidelines
 

Patients on IV steroids may be switched to an equivalent dose of oral corticosteroids (e.g. prednisone) at start of tapering or earlier, once sustained clinical improvement is observed. Lower bioavailability of oral corticosteroids should be taken into account when switching to the equivalent dose of oral corticosteroids.

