**6.13 Dose Modifications for Renal Adverse Events**

Dose modifications for renal adverse events will be per [Section 6.2](#) if DLT definition is met. Refer to algorithm below for recommended management guidelines.

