## 8.0 EVALUATIONS/MATERIAL AND DATA TO BE ACCESSIONED

### 8.1 Required Clinical, Laboratory and Disease Evaluation

All clinical and laboratory studies to determine eligibility must be performed within 7 days prior to enrollment unless otherwise indicated. Laboratory values used to assess eligibility (see [Section 4.0](#)) must be no older than seven (7) days at the start of therapy. Laboratory tests need **not** be repeated if therapy starts **within** seven (7) days of obtaining labs to assess eligibility. If a post-enrollment lab value is outside the limits of eligibility, or laboratory values are older than 7 days, then the following laboratory evaluations must be re-checked within 48 hours prior to initiating therapy: CBC with differential, bilirubin, ALT (SGPT) and serum creatinine. If the recheck is outside the limits of eligibility, the patient may not receive protocol therapy and will be considered off protocol therapy. Imaging studies must be obtained within 14 days prior to start of protocol therapy (repeat the tumor imaging if necessary).

STUDIES TO BE OBTAINED	Pre-Study	During Cycle 1	Prior to Subsequent Cycles ^
History	X	Weekly	X
Physical Exam with vital signs	X	Weekly	X
Height, weight, BSA	X		X
Performance Status	X		X
Pregnancy Test 	X		
CBC, differential, platelets	X	Weekly 	Weekly 
Urinalysis	X		X
Electrolytes including Ca ++ , Cl, PO 4 , Mg ++	X	Weekly	X
Creatinine, ALT*, AST*, bilirubin	X	Weekly	X
Amylase, lipase, CRP	X		X
TSH 	X	End of Cycle 1	X
Tumor Disease Evaluation- Parts A and B	X	End of Cycle 1	End of cycle 2, then q 3 cycles 
Tumor Disease Evaluation- Parts C, D, and E	X	End of Cycle 2	End of cycle 4, then q 3 cycles 
Pulse Oximetry	X		With Tumor Disease Evaluation
Pharmacokinetics  (Required)	X	X 	X
Vaccine Antibody and Cytokine Studies  (Optional)	X	X	X
Anti-Drug Antibody (ADA)  (Required)	X	X	X
Tumor Tissue (Required, if available)	X 		X 
EKG  , ECHO 	X	Clinically Indicated	
CPK and Troponin 	X	Clinically Indicated	

^ Studies may be obtained within 72 hours prior to the start of the subsequent cycle.

\* For the purpose of this study, the ULN for SGOT (AST) is 50 U/L and the ULN for SGPT (ALT) is 45 U/L.

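### From Cycle 5 in Part E, no liver or renal chemistry is required before the Day 15 nivolumab dose, so the Section 6.5 hold has no required result to act on for a new silent liver rise

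*Combined protocol and SAP*

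**What the plan says.** **Dosing.** Under Section 5.1.5, Part E gives the combination on Day 1 of four 21-day cycles. From Cycle 5 it gives nivolumab alone at 3 mg/kg "on days 1 and 15 of each cycle", and cycles are 28 days long.

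**Testing.** In the Section 8.1 table the row "Creatinine, ALT*, AST*, bilirubin" is marked for pre-study, weekly in Cycle 1, and once in the column for later cycles. The footnote to that column reads "Studies may be obtained within 72 hours prior to the start of the subsequent cycle". In the same column the CBC row is marked weekly. None of the numbered footnotes adds chemistry at Day 15.

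**Gate for re-treatment.** Section 5.2 lets a cycle be repeated "if the patient has again met the parameters as defined in the eligibility section". That condition attaches to starting a cycle, not to a dose within it.

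**Rule for the next dose.** The liver table in Section 6.5 says for Grade 2: "Hold until baseline. If resolves within 7 days, resume at same" dose level. Grade 3 and 4 mean removal from therapy, apart from the exceptions in Section 5.4.1. The same section warns: "Continued treatment of active immune mediated hepatitis may exacerbate ongoing inflammation".

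**Suggested algorithms.** Section 6.5.1 tells sites, for Grade 1 and again for a Grade 2 that has returned to baseline: "Continue routine LFT monitoring per Table 8.1". Section 6.13 begins "Dose modifications for renal adverse events will be per" and points to Section 6.2 where the DLT definition is met. The hold for Grade 2 or 3 creatinine appears only in the recommended algorithm of Section 6.13.1.

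**The concern.** The Section 6.5 liver rules are triggered by laboratory values (Appendix IX gives the cut-offs), so a rise without symptoms can be acted on only if someone has measured it. From Cycle 5 the plan schedules a dose in mid-cycle but no chemistry to go with it. After Cycle 1, history and physical examination are also required only once per cycle, so there is no required clinical checkpoint at Day 15 either.

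A child whose ALT has silently reached Grade 2 or more since Day 1 could thus receive a dose that Section 6.5 says to withhold, in a setting where the protocol itself says continued treatment may make hepatitis worse. A rise that is already known is handled: it triggers the hold, and Section 6.5.1 suggests testing every 3 days from Grade 2. The gap is confined to a new or worsening rise that nobody has yet measured.

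The protocol gives some reason to take late liver events seriously. In the adult randomised melanoma trial of the same regimen (Section 2.3), treatment-related Grade 3-4 ALT increase occurred in 10 of 94 patients (11%). The paediatric ipilimumab trial (Section 2.4) saw immune events as late as week 36, though most came in the first three weeks.

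**Working it through.** The plan states no figure on this point, so there is none to reproduce. The check compares the testing schedule with the dosing schedule.

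**Inputs**
- Chemistry after Cycle 1: once per cycle, 0 to 3 days before Day 1 (Section 8.1 table and its footnote).
- Part E, Cycles 1-4: 21 days each, dosing on Day 1 only (Section 5.1.5).
- Part E, Cycle 5 onward: 28 days, dosing on Days 1 and 15 (Section 5.1.5).
- Permitted delay of a scheduled dose: up to 7 days (Section 5.2).
- Maximum Part E enrolment: 23 (Section 11.7.1).

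**Age of the newest required panel at dosing**
- Cycles 2-4, Day 1: 0 to 3 days.
- Cycle 5 onward, Day 1: 0 to 3 days.
- Cycle 5 onward, Day 15: (15 − 1) + 0 to 3 = 14 to 17 days.
- If the Day 15 dose is itself delayed by the full 7 days: up to 14 + 3 + 7 = 24 days.

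**Doses affected.** One of the two doses in each cycle from Cycle 5 has no required pre-dose panel, so half of scheduled doses.

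**Interval between required panels**
- Cycles 2-4: 21 ± 3 = 18 to 24 days.
- Cycle 5 onward: 28 ± 3 = 25 to 31 days, with one Day 15 dose inside each interval.

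**Time from an on-time Day 15 dose to the next required panel.** The next cycle starts on Day 29 and its panel falls on Days 26 to 29, so 26 − 15 = 11 to 29 − 15 = 14 days.

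**When the gap opens.** Cycles 1-4 last 4 × 21 = 84 days, or 12 weeks, so Cycle 5 starts at about week 13. At that point scheduled nivolumab goes from 1 mg/kg every 3 weeks to 3 mg/kg every 2 weeks, while the required chemistry interval lengthens from about 21 to about 28 days.

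**Does another section close the gap?**
- Section 5.2 gates the start of a cycle only.
- Section 6.5 says what to do with a result but does not call for one.
- Section 6.5.1 sends routine monitoring back to the Section 8.1 table and raises the frequency only after Grade 2 has been found.
- Section 7.3 covers work-up once liver toxicity is suspected from raised tests or symptoms.
- Sections 6.13 and 6.13.1 add no scheduled Day 15 creatinine.

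The number of required panels between the Day 1 dose and the Day 15 dose is therefore zero.

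**The case against.** The facts are not in dispute; the case against concerns how much they matter.

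- **Deliberate design.** Chemistry is scheduled by cycle throughout, and the Section 5.2 gate uses the same unit. Parts A and B used the same table with Day 1 and Day 15 dosing, and Section 11.1 records 13 + 72 = 85 patients enrolled in them. This shows consistency, but it does not supply a result on which to apply the Section 6.5 rule.
- **Lower-intensity phase.** Ipilimumab has stopped by Cycle 5. Section 2.3 puts autoimmune reactions at about 30% with anti-CTLA4 and below 10% with anti-PD1, and most events in the paediatric ipilimumab trial came early. This stands and lowers the expected number of events. It does not remove late ones.
- **Choice of comparison.** Panel age at dosing (14 to 17 days against 0 to 3) is more striking than the interval between panels (about 28 days against about 21). Both are fair. The first governs whether the hold can operate before the dose; the second governs how long a rise can go unseen.
- **No event rate.** The documents do not say how often a silent Grade 2 or higher rise would appear between Day 1 and Day 15 after Cycle 4, or how many patients will reach Cycle 5. That stands; the number may be very small.
- **Lipase has the same gap.** Section 6.5 also holds for Grade 2 lipase, which is tested no more than once per cycle. This is correct, and it argues for widening the fix.
- **The weekly CBC is not tied to Day 15.** This is also correct, so the new test needs its own timing window.
- **The renal half is weaker.** The Grade 2-3 creatinine hold is only recommended, and the binding renal rule works through the DLT definition.

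**Conclusion.** The concern holds. From Cycle 5 in Part E, the plan as written requires no liver or renal chemistry before the Day 15 dose, and no other section supplies it. The binding Section 6.5 rule therefore has no required result for a new asymptomatic liver rise at half of the scheduled doses. Creatinine has the same testing gap, with a weaker rule behind it.

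The 14-to-17-day figure assumes on-time dosing and chemistry drawn only when required; a site that tests more often by its own practice has no gap. Exposure is limited to Part E patients still on therapy after 12 weeks, out of at most 23. Parts A to D are marked completed, so Part E is where a change can still help.

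This is a patient-safety point. The Part E toxicity stopping rule in Section 11.7.1 counts Cycle 1 DLTs, when chemistry is weekly, so no trial conclusion changes. It should be corrected because the remedy is cheap, not because many events are expected.

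**What to change.** Add a footnote to the chemistry row of the Section 8.1 table: *From Cycle 5 in Part E, creatinine, ALT, AST and bilirubin are also required within 72 hours before each Day 15 dose, and the result is reviewed before the infusion starts.* State in Section 6 that the hold and off-therapy rules apply to that result. Consider including lipase, which has the same gap.

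The cost is one extra panel per 28-day cycle. It can share the weekly CBC draw if that draw is timed inside the 72-hour window; otherwise it can be taken at the infusion visit, with the result back before dosing. No extra visit is needed. Some Day 15 doses will be held for rises that prove transient, which is what Section 6.5 already prescribes for a known rise.

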 Women of childbearing potential require a negative pregnancy test prior to starting treatment. Men and women must be willing to adhere to effective contraception during the study and for 5 months after the last dose of nivolumab for women of childbearing potential and 7 months after the last dose of nivolumab for men sexually active with women of childbearing potential. Abstinence is an acceptable method of birth control.

 If patients have Grade 4 neutropenia then CBCs should be checked at least every other day until recovery to Grade 3 or until meeting the criteria for dose limiting toxicity.

- 3 If patients develop Grade 4 neutropenia then CBCs should be checked every 3 to 4 days until recovery to Grade 3
- 4 Free T4 should also be measured for patients with an abnormal TSH level. Guidance on the management of patients who develop hypothyroidism is included in [Section 7.3.4](#).
- 5 Tumor Disease Evaluation should be obtained on the next consecutive cycle after initial documentation of either a PR or CR. Please note that if the institutional investigator determines that the patient has progressed based on clinical or laboratory evidence, he/she may opt not to confirm this finding radiographically. If tumor growth is > 20% but < 40%, imaging to include target lesions must occur every cycle if clinically indicated, or if “pseudoprogression” appears based on inflammatory response, and the same radiographic and clinical criteria must be met in order to remain on study (See [Section 12.2.1](#)).
- 6 See [Section 8.3.2](#) and [Appendix III](#) for timing of PK studies.
- 7 Patients who are removed from therapy during Cycle 1 after receiving the dose of nivolumab on Day 15 should have their last PK sample collected on Day 28 of Cycle 1.
- 8 See [Section 8.4.2](#) and [Appendix IV](#) for timing of vaccine antibody and section [8.8.2](#) and [Appendix VII](#) for timing of cytokine studies.
- 9 See [Section 8.5.2](#) and [Appendix V](#) for timing of ADA studies.
- 10 See [Section 8.6](#) and [Appendix VI](#) for instructions for submitting tumor specimens. If tissue blocks or slides are unavailable, the study chair must be notified prior to study enrollment.
- 11 In the event a subject requires a biopsy for surgery and tumor tissue is removed, tissue will be requested for PD-L1 and CD8 Expression analysis (required, if available).

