### 11.2.3 Evaluability for Response

Any patient who is enrolled who meets eligibility criteria for Parts B, D or E and receives at least one dose of protocol therapy will be considered evaluable for response provided: (1) the patient demonstrates progressive disease or death while on protocol therapy (note: if the institutional investigator determines that the

patient has progressed based on clinical or laboratory evidence, he/she may opt not to confirm this finding radiographically); or (2) the patient is observed on protocol therapy for at least one cycle and the tumor is not removed surgically prior to the time complete response or partial response is confirmed, or (3) the patient demonstrates a complete or partial response as confirmed according to protocol criteria. Patients who demonstrate a complete or partial response confirmed by central review will be considered to have experienced a response for the application of the rule given in Section 11.4. Two objective status determinations are required to confirm best response ([Section 12.6](#)). All other patients will be considered non-responders. All patients considered to have a response (CR or PR) must have imaging studies reviewed centrally at the COG. Centers will be notified by the COG about requests for scans of patients with stable disease. See [Section 8.2](#) regarding image submission instructions. The central review by COG will be provided as the final reviewed assessment of response when such becomes available. Patients inevaluable for response will be considered for replacement.

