**11.7 Phase 2 Evaluation of Nivolumab (1 mg/kg) in Combination with Ipilimumab (3 mg/kg) (for Part E):**

**11.7.1 Study Design**

The Simon’s optimal two stage design will be used for Part E to assess response in rhabdomyosarcoma (E3) and Ewing/Peripheral PNET pediatric patients (E4). All patients enrolled into either E3 or E4 will be combined for assessment of response and toxicity. Assuming that the study does not stop early for dose limiting toxicity, a total of 10 response-evaluable patients will be enrolled into Stage 1. This will include at least 4 patients each in parts E3 and E4. If at least 1 response is observed among 10 evaluable patients, then stage 2 will open for enrollment. A total of 10 more response-evaluable patients will then be enrolled into Stage 2 including at least 4 more patients each in parts E3 and E4. Otherwise, the study will close with stage 1 and the study will conclude that the agent does not elicit sufficient response.

The following Simon’s optimal two-stage design will be used to assess response in Part E.

	Cumulative Number of Responses	Decision
Stage 1: Enter 10 patients	0	Terminate the stratum: agent ineffective
	1 or more	Inconclusive result, continue stratum

		(proceed to stage 2)
Stage 2: Enter 10 additional patients	2 or less	Terminate the stratum: agent ineffective
	3 or more	Terminate the stratum: agent effective

The combination of Nivolumab (1 mg/kg) and Ipilimumab (3mg/kg) will not be considered of sufficient interest for further evaluation among Rhabdomyosarcoma and Ewing/Peripheral PNET patients if the true response rate is  $\leq 5\%$  and of sufficient activity if the true response rate is  $\geq 25\%$ . If this combination has a true response rate of 5%, the rule described above will identify it of sufficient activity for further study with probability 0.07 (type I error), and the trial will have an expected sample size of 14 with 60% probability of early termination. If the combination has a true response rate of 25%, the rule described above will identify it of sufficient activity for further study with probability 0.88 (power against the alternative hypothesis  $P = 0.25$ ). A maximum of 23 patients will be enrolled into Part E allowing for 10% inevaluability.

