#### 11.7.2 Method of Analysis

Response criteria are described in [Section 12.0](#). Response rates will be calculated for the combined cohort as the percent of patients whose best response is a CR or PR and confidence intervals will be constructed according to the method of Chang. A responder is defined as a patient who achieves a best confirmed response (as defined in [Section 12.6](#)) of PR or CR on the study and includes pseudo-progressive disease. Response is defined relative to baseline disease.

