**12.6 Best Response**

Evaluation of Best Overall Response

The best overall response is the best response recorded from the start of the treatment until disease progression/recurrence (taking as reference for progressive disease the smallest measurements recorded since the treatment started). The patient's best response assignment will depend on the achievement of both measurement and confirmation criteria.

Table 1: For Patients with Measurable Disease (i.e., Target Disease)

Target Lesions	Non-Target Lesions	New Lesions	Overall Response	Best Overall Response when Confirmation is Required*
CR	CR	No	CR	$\geq 28$ days Confirmation**
CR	Non-CR/Non-PD	No	PR	$\geq 28$ days Confirmation**
CR	Not evaluated	No	PR	
PR	Non-CR/Non-PD/not evaluated	No	PR	
SD	Non-CR/Non-PD/not evaluated	No	SD	documented at least once $\geq 28$ days from baseline**
PD	Any	Yes or No	PD	no prior SD, PR or CR
Any	PD***	Yes or No	PD	
Any	Any	Yes	PD	

\* See RECIST 1.1 manuscript for further details on what is evidence of a new lesion.

\*\* Only for non-randomized trials with response as primary endpoint.  
 \*\*\* In exceptional circumstances, unequivocal progression in non-target lesions may be accepted as disease progression.  
**Note:** Patients with a global deterioration of health status requiring discontinuation of treatment without objective evidence of disease progression at that time should be reported as “*symptomatic deterioration*.” Every effort should be made to document the objective progression even after discontinuation of treatment.

Table 2: For Patients with Non-Measurable Disease (i.e., Non-Target Disease)

Non-Target Lesions	New Lesions	Overall Response
CR	No	CR
Non-CR/non-PD	No	Non-CR/non-PD*
Not all evaluated	No	not evaluated
Unequivocal PD	Yes or No	PD
Any	Yes	PD
* ‘Non-CR/non-PD’ is preferred over ‘stable disease’ for non-target disease since SD is increasingly used as an endpoint for assessment of efficacy in some trials so to assign this category when no lesions can be measured is not advised		

Table 3. Sequences of overall response assessments with corresponding best response.

1 st Assessment	2 nd Assessment	Best Response
Progression		Progressive disease
Stable, PR, CR	Progression	Progressive disease
Stable	Stable	Stable
Stable	PR, CR	Stable
Stable	Not done	Not RECIST classifiable
PR	PR	PR
PR	CR	PR
PR, CR	Not done	Not RECIST classifiable
CR	CR	CR

Table 4: Overall Response for Patients with Neuroblastoma and Measurable Disease

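### In Part E's 21-day cycles, the confirmatory scan for a response first seen at end of Cycle 2 comes 21 days later, short of the 28-day minimum in Section 12.6 Table 1, while Table 3 states no interval

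*Combined protocol and SAP*

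**What the plan says.** **Schedule.** Section 5.1.5 sets 21-day cycles for Cycles 1 to 4 of Part E and 28-day cycles from Cycle 5. The Section 8.1 table places tumor evaluations for Parts C, D and E at end of Cycle 2, end of Cycle 4 and every three cycles after that. It allows studies up to 72 hours before the next cycle starts. Footnote 5 adds: "Tumor Disease Evaluation should be obtained on the next consecutive cycle after initial documentation of either a PR or CR". Section 12.2 calls this extra scan confirmatory and places it at the end of the cycle after the one in which response was first documented.

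**Confirmation.** Section 12.6 says a patient's "best response assignment will depend on the achievement of both measurement and confirmation criteria". Its Table 1 gives 28 or more "days Confirmation" for CR and PR, with the footnote "Only for non-randomized trials with response as primary endpoint". Part E is non-randomized, and antitumor effect in Parts D and E is a primary aim (Section 1.1), so the footnote applies. Table 3, titled "Sequences of overall response assessments with corresponding best response", maps PR then PR to PR and CR then CR to CR, with no minimum interval.

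**Use.** Section 11.2.3: "Two objective status determinations are required to confirm best response", with a reference to 12.6. Section 11.7.2: "A responder is defined as a patient who achieves a best confirmed response" of PR or CR, again as defined in 12.6. Section 11.7.1: "If at least 1 response is observed among 10 evaluable patients, then stage 2 will open for enrollment". After stage 2, three or more responses in 20 count as effective and two or fewer as ineffective.

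**The concern.** The scan that the protocol names as confirmatory is scheduled too early to meet the protocol's own confirmation interval. The next-cycle rule gives a nominal 28 days where cycles last 28 days, as in Parts A and B. It gives 21 where cycles last 21 days.

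Table 3, read alone, accepts two consecutive PRs at any spacing. Table 1 does not. A patient with PR at days 42 and 63 and no later confirming scan is therefore unconfirmed under one table and a PR under the other. Part E's decisions can rest on a single response. If such a patient appeared, the rule would have to be settled after the outcome was known.

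**Working it through.** **1. The plan's own figures.** The Part E design stops at 0 of 10 and declares activity at 3 or more of 20. With X1 and X2 independent binomial counts on 10 patients each:

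P(declare active) = 1 − P(X1=0) − P(X1=1)·P(X2≤1) − P(X1=2)·P(X2=0)

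- At 5%: 1 − 0.5987 − 0.3151×0.9139 − 0.0746×0.5987 = 0.0686 (stated 0.07).
- At 25%: 1 − 0.0563 − 0.1877×0.2440 − 0.2816×0.0563 = 0.8820 (stated 0.88).
- Early termination at 5%: 0.95^10 = 0.5987 (stated 60%). Expected size: 10 + 10×(1 − 0.5987) = 14.01 (stated 14).

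All reproduce. They presuppose an unambiguous count of responders.

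**2. Scan days.** Cycles 1 to 5 start on days 1, 22, 43, 64 and 85. Cycle 5 lasts 28 days, so Cycle 6 starts on day 113.

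| Scan | Nominal day | With 72-hour window |
|---|---|---|
| End of Cycle 2 | 42 | 40–43 |
| End of Cycle 3 | 63 | 61–64 |
| End of Cycle 4 | 84 | 82–85 |
| End of Cycle 5 | 112 | 110–113 |

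**3. Interval to the prescribed confirmatory scan, first response at end of Cycle 2.**

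- Nominal: 63 − 42 = 21 days, short by 28 − 21 = 7.
- With the window: 61 − 43 = 18 to 64 − 40 = 24 days, short by 4 to 10.
- With a full 7-day cycle delay (Section 5.2): 18 + 7 = 25 to 24 + 7 = 31 days. A delay of at least 4 days, with favorable scan timing, is needed to reach 28.

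**4. Other routes to confirmation.**

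- Routine end-of-Cycle-4 scan: 84 − 42 = 42 days (82 − 43 = 39 to 85 − 40 = 45). This meets Table 1.
- Off therapy, Section 8.1.1 requires an evaluation about 100 days after the last nivolumab dose. Last dose on day 43: day 143, which is 101 days after day 42. Last dose on day 64: day 164, which is 122 days after. Under Section 12.2.2.1 it helps only if no other anti-cancer therapy has begun.

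**5. First response at end of Cycle 4.** The next-cycle scan is nominally 112 − 84 = 28 days later, so there is no conflict on the nominal schedule. With the window it is 110 − 85 = 25 to 113 − 82 = 31 days. This matters for how the fix is worded.

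**6. Who is left.** Doubt remains only for a patient with PR or CR at about days 42 and 63, followed by progression, other anti-cancer therapy or no usable scan before any assessment that meets the 28 days.

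**The case against.** The strongest reply is that the plan already copes. Section 12.2 makes the confirmatory scan additional to the scheduled ones, so the end-of-Cycle-4 scan still takes place and confirms any response that persists on therapy. Leaving therapy does not by itself prevent confirmation, because of the evaluation at about 100 days. This stands, and it makes the affected group small.

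Second, the opening of 12.6 puts confirmation criteria ahead of all its tables, and Table 1 gives the only interval for CR and PR. It can fairly be read as governing Table 3. That is the better reading, but no text says so. Even on that reading, the prescribed scan misses the interval on an undelayed schedule.

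Third, central review gives the final response assessment (11.2.3), and opening stage 2 is discussed with the DSMC and NCI (11.7.1). Neither safeguard supplies an interval, so neither settles the classification.

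Fourth, in the text available the 28-day entry sits on the CR row and the first PR row. Its application to the ordinary PR row rests on reading a merged cell. That is plausible but remains an assumption.

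A reader might infer that early responders are generally lost, or that the stated power of 0.88 is too high. The documents do not support this: a persisting response is confirmed later, and nothing says how often the ambiguous case arises. A reader might also carry the point to Part D, which used the same cycles. Part D is closed, no stage decision there is affected, and the one PR reported from it (Section 2.4) has no scan dates.

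**Conclusion.** The inconsistency is real and confined to Part E: a nominal 21 days (18 to 24 with the window) against a required 28 or more. Its importance is minor to moderate. The stated operating characteristics are correct, and no change to them is claimed. What is at stake is one patient's classification at 0 versus 1 of 10 or 2 versus 3 of 20.

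This rests on three conditions: the merged-cell reading of Table 1; a patient who responds at both early scans and has no later qualifying one; and Part E not having already been closed by its toxicity rule in 11.7.1.

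**What to change.** 1. In Section 12.6, state that Table 1's minimum of 28 days also governs the Table 3 sequences. Cite it in 11.2.3 and 11.7.2.
2. In Section 8.1 footnote 5 and Section 12.2, replace the next-cycle timing for Part E patients with a confirmatory scan at least 28 days after the scan that first documented response. For responses first seen at end of Cycle 2, set it no later than the end-of-Cycle-4 scan, nominally days 70 (42 + 28) to 84. For responses first seen at end of Cycle 4 or later, set the scan window so that a gap of 25 to 27 days cannot occur.

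**Cost.** The change is to wording in five places. For an end-of-Cycle-2 response, one scan moves by 70 − 63 = 7 to 84 − 63 = 21 days and may fall off a cycle boundary; at its latest it is the scan already scheduled for end of Cycle 4. A response documented only over 21 to 27 days would not count. No scan is added for patients who have left protocol therapy. Because 12.6 serves every part, the new sentence should say that it is added for Part E.
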